### 6.6.1. Permitted Medicines

#### Analgesics:

Subjects will be required to restrict if possible the use of analgesic to ibuprofen or acetaminophen/paracetamol for the duration of the study, from the screening to the Week 36 visit. Standard doses of ibuprofen and acetaminophen/paracetamol will be provided free of charge to the subject. The subject eDiary will include selection-boxes for ibuprofen, acetaminophen/paracetamol or other, including dosage. The analgesics provided will be used only as rescue medication; no prophylactic use of analgesics is allowed during the whole study.

#### Contraceptive use:

For subjects of childbearing potential and requiring contraception, non-hormonal contraception is required from beginning of screening period until end of treatment. Two forms of non-hormonal contraception will be required e.g. condom with spermicide. Suitable condoms with spermicide will be provided free of charge to subjects over the duration of the study.

After the end of treatment period (end of week 24) until the end of follow-up period, no contraception is required. For subjects wanting a contraceptive method, a single form of non-hormonal contraception is sufficient.

Hormonal contraception is prohibited from beginning of screening period until end of week 36.

OBE2109 could potentially induce CYP3A4 at high concentrations which are not expected with doses up to 200 mg daily. However, Investigators should note this potential induction of CYP3A4 in case that subjects taking drugs metabolised by CYP3A4 experience attenuation of their effects and should consider a dose adjustment of the CYP3A4 substrate or discontinuation of OBE2109 as appropriate.

Any medications other than those excluded by the protocol (see section 5.2.2 or 6.6.2), which are considered necessary for the subject's welfare and/or which will not interfere with the study medication, may be given at the discretion of the Investigator.

**6.6.2. Prohibited Medicines**

Medication listed in exclusion criteria (see Section 5.2.2) will be prohibited up to week 36.

To consider a subject who is currently taking any prohibited therapies for potential inclusion in this study, the Investigator must ensure that the subject has sufficient washout time prior to enrolling the subject (see Section 5.2.2).

Substrates of cytochrome P450 2C8 (CYP2C8) (e.g. montelukast, repaglinide) and of organic anion transporter 3 (OAT3) (e.g. benzylpenicillin, sitagliptin, ciprofloxacin, pravastatin, rosuvastatin) are prohibited during the treatment period only.

When a prohibited medication or treatment is necessary for the subject's well-being, the sponsor must be notified and possible alternatives are to be discussed before administration of the prohibited medication or treatment whenever possible.

**6.6.3. Non-Drug Therapies**

Not applicable.

**6.7. SUBJECT COMPLETION AND WITHDRAWAL****6.7.1. Subject Completion**

A subject will be considered as a "completer" when she has completed all study procedures at visit Week 24 as described in the protocol. The end of Part B visit on Week 24 constitutes subject completion (see APPENDIX A).

Subjects who did not receive the study drug will be withdrawn from the study and no further study procedures will be performed. The eCRF exit form should be completed.

**6.7.2. Subject Withdrawal from Study**

Subjects will be informed that they have the right to withdraw from the study at any time, without prejudice to their medical care, and that they are not obliged to state the reason(s). Any withdrawal must be fully documented in the eCRF exit form and should be followed up by the Investigator.

The Investigator may withdraw a subject at any time if this is considered to be in the subject's best interest.

In addition, the sponsor could make a decision to temporarily or permanently discontinue the study for safety, ethical, compliance or other reasons. In this case, the subject's participation may be ended prematurely without asking for her consent.

Subjects discontinuing participation in the study between Day 1 and Week 24 visits should undergo the procedures required at Week 24 visit. Subjects discontinuing participation in the study between Week 24 and Week 36 visits should undergo the procedures required at Week 36 and Week 48 visits. Subjects discontinuing participation in the study between Week 36 and Week 48 visits should undergo the procedures required at Week 48 visit.

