**6.2.3.2. Study visit Week 24 (Day 169 ± 3 days) – End-of-Part B visit**

The subject will take her daily dose at the usual time in the morning at home.

The following tests and evaluations will be performed at week 24 Study Visit:

- Weight
- Assessment of endometriosis pain with the mB&B scale (see APPENDIX B)
- Previous and concomitant treatments recording
- AE recording
- Physical examination
- Vital signs (blood pressure and heart rate)
- Gynecological examination, including the mB&B scale (see APPENDIX B) clinical signs reporting (pelvic tenderness and pelvic induration)
- TVUS of uterus for measuring endometrium thickness and of ovaries for checking their normality
- Urine pregnancy test
- Contraception counselling
- eDiary check for good completion
- EHP-30 (see APPENDIX C) and PGIC (see APPENDIX D) questionnaires completion by the subject
- Post-dose PK samples (the approximate time of dose administration at home and time of taking of the PK sample will be recorded)
- Blood samples for haematology, coagulation parameters, chemistry, lipids, hormones

- Urinary protein dipstick
- Endometrium biopsy, unless the endometrium thickness in TVUS is  $\leq 5$  mm, in which case no endometrium biopsy will be necessary, as far as the screening biopsy has provided assessable results. Appropriate photo documentation of the endometrium thickness is mandatory.
- BMD assessed by DXA for femoral neck, hip and spine. DXA can be performed  $\pm 10$  days from study visit.
- The subject will be verbally asked which treatment she believed she received during the blinded treatment period. The answer will be recorded in the eCRF.

Study visit Week 24 constitutes the end of Part B visit.

The subject will be proposed to continue in an extension study. If the subject accepts, the eCRF exit form will be completed and the subject will stop the current study and continue in the extension study (see section 6.2.5).

Otherwise the subject will continue in the treatment-free follow-up period.

**6.2.4. Follow-up period without treatment – Study visits Week 28 (Day 197  $\pm$  3 days), Week 36 (Day 253  $\pm$  3 days) and Week 48 (Day 309  $\pm$  3 days)**

Up to week 36 study visit, the subject will be asked to record on her eDiary:

- Daily, at approximately the same time each evening, her IMP intake, pelvic pain, dyspareunia, difficulty in performing daily activities, uterine bleeding and use of analgesic drug(s) including dose;
- Weekly, her dyschezia pain;

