**6.2.4.3. Study visit Week 48 (Day 309 ± 3 days) – End of Follow-up visit**

The following evaluation will be performed at Week 48 Study Visit:

- BMD assessed by DXA for femoral neck, hip and spine. DXA can be performed ± 10 days from study visit.
- AE recording if related to BMD loss
- Previous and concomitant treatments recording only if treatments with potential impact on BMD
- Completion of the eCRF exit form

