**6.7.2.1. Discontinuation criteria**

During the course of the study, the subject may be discontinued for the following reasons:

- **Lack of Efficacy:** Investigator's judgment only. If subject's opinion only, check subject's Request. Explain in the comment section of the eCRF Exit Form.
- **Adverse Event:** Includes clinically significant new or worsening existing condition as judged by the Investigator. Document in the AE form.
- **Subject's Request:** Consent withdrawal, subject moved, schedule conflicts, etc. Specify the reason in the comment section of the eCRF Exit Form.
- **Protocol Violation:** Major protocol violation which may affect the subject's safety. Specify the protocol violation in the comment section of the eCRF Exit Form.
- **Lost to Follow-up:** Document with two phone calls and a certified letter requesting return receipt without response. Document in the comment section of the eCRF Exit Form.
- **Pregnancy:** Subjects that have been exposed to study treatment and who become pregnant during the treatment period will be immediately withdrawn from treatment. Pregnancies that have been exposed to study treatment and occurred up to week 36, or started up to 4 weeks after treatment discontinuation in case of early withdrawal will be followed up for pregnancy and neonatal outcomes at birth. Any pregnancy must be reported with the Pregnancy Surveillance Form (see section 8.6).
- **Other:** Specify in the Comments section in the eCRF Exit Form. This reason should only be used if the reason for discontinuation is not better accounted for by another category.

Subjects who have an elevation of hepatic enzymes suspicious of drug induced liver toxicity according to the Food and Drug Administration (FDA) guidance on drug-induced liver injury (26), i.e. LFT increase > 3 x ULN associated with increased bilirubin > 1 x ULN, will be immediately withdrawn from treatment and followed up to return to normal of hepatic parameters.

All subjects withdrawn from treatment will enter – if appropriate – a 24-week follow-up period without treatment and continue daily eDiary recording up to Week 36 visit in order to continue to collect efficacy data.

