**6.7.2.2. Follow-up for discontinued subjects**

Not applicable.

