**III - CONTRAINDICATIONS****Suspected pregnancy:**

Evidence of an on-going pregnancy provided by an ultrasound examination or serum hCG levels is an absolute

contraindication to using the Pipelle de Cornier®. As a precautionary measure, it is therefore advisable to rule out a pregnancy in women with childbearing potential and not using an effective method of contraception, by performing a serum hCG assay and an ultrasound examination less than 15 days prior to the endometrial biopsy.

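### Read literally, the discontinuation and follow-up rules can direct a woman discontinued for pregnancy to a Pipelle biopsy, which the protocol's own Appendix E contraindicates

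*Combined protocol and SAP*

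**What the plan says.** **Discontinuation.** Protocol section 6.7.2 has one rule for everyone who leaves before Week 24: "Subjects discontinuing participation in the study between Day 1 and Week 24 visits should undergo the procedures required at Week 24 visit". Nothing in it depends on why the subject leaves.

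**Pregnancy.** Section 6.7.2.1 lists pregnancy among the reasons for discontinuation: "Subjects that have been exposed to study treatment and who become pregnant during the treatment period will be immediately withdrawn from treatment". The section ends with a general rule: "All subjects withdrawn from treatment will enter – if appropriate – a 24-week follow-up period without treatment".

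**Biopsy at Week 24.** Section 6.2.3.2 lists "Endometrium biopsy, unless the endometrium thickness in TVUS is" 5 mm or less, provided that the screening biopsy could be assessed. Appendix A footnote 2 repeats this waiver.

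**Biopsy at Week 36.** Section 6.2.4.2 and Appendix A footnote 3 call for a biopsy if none was obtained at Week 24, or if the Week 24 diagnosis was anything other than benign. The footnote is worded as mandatory.

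**Device.** Section 6.4.3 specifies the Pipelle de Cornier and refers to Appendix E. Under contraindications, Appendix E says: "Evidence of an on-going pregnancy provided by an ultrasound examination or serum hCG levels is an absolute" contraindication to using the device.

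**Where an exception might be expected.** Section 6.7.2.2, headed "Follow-up for discontinued subjects", is marked as not applicable. Section 8.6 deals with withdrawal from the study drug and with reporting and following the pregnancy. It does not mention the biopsy.

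**The concern.** Pregnancy is one of the discontinuation reasons that the protocol itself foresees, so the rule for leaving the study should work for it. As written, the rule passes the subject to a list of procedures of which one is contraindicated by an appendix that the protocol invokes. Sites would have to notice the conflict and decide which text prevails, and different sites could decide differently. What is at stake is the safety of a small group of women and the clarity of the instructions to sites. A site that follows Appendix E would also be departing from the visit list, with no text to say whether that counts as a deviation.

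**Working it through.** No sample size, power or error rate bears on this point. The check is to follow a woman found to be pregnant between Day 1 and Week 24 through the text.

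1. **Is she discontinued?** Section 6.7.2.1 puts pregnancy in the list of discontinuation reasons, but the wording under that entry is withdrawal from treatment. Section 8.6 likewise speaks of withdrawal from the study drug. Two readings are possible.

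2. **Route A: she discontinues participation.** Section 6.7.2 sends her to the Week 24 procedures. Section 6.2.3.2 then lists the biopsy. The only waiver has two conditions, an endometrium of 5 mm or less and an assessable screening biopsy. Neither concerns pregnancy. The same list includes a urine pregnancy test and a transvaginal ultrasound, but no consequence for the biopsy is stated if either shows a pregnancy.

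3. **Route B: she is withdrawn from treatment and enters follow-up.** Entry is qualified in section 6.7.2.1, which leaves room for judgement. Once she is in follow-up, Appendix A footnote 3 applies. If no biopsy was obtained at Week 24, for whatever reason, one is mandatory at Week 36. Withholding the Week 24 biopsy because of the pregnancy therefore triggers the Week 36 requirement. The visits are 12 weeks apart by label and 253 − 169 = 84 days apart by the printed visit days. Whether the pregnancy is still ongoing at Week 36 depends on its timing and outcome, which the documents cannot settle. Neither section 6.2.4.2 nor the footnote makes an exception if it is.

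4. **What does the device appendix say?** Section 6.4.3 ties the biopsy to the Pipelle and to Appendix E, and Appendix E makes ongoing pregnancy an absolute contraindication.

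5. **Is there an exception elsewhere?** Section 6.7.2.2 has no content. Section 8.6 gives no exemption from any procedure.

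| Route | Text that calls for a biopsy | Stated way out | Covers pregnancy? |
|---|---|---|---|
| A, Week 24 | 6.7.2 with 6.2.3.2 | Endometrium of 5 mm or less and assessable screening biopsy | No |
| B, Week 36 | 6.2.4.2 and Appendix A footnote 3 | Follow-up judged not appropriate, or a benign Week 24 biopsy | Not by name |

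A smaller mismatch appears on the way. The pregnancy entry in section 6.7.2.1 says that every pregnancy is to be reported on the surveillance form and refers to section 8.6. Section 8.6 requires the form for pregnancies conceived up to Week 36, or up to 4 weeks after the last dose in subjects who terminate early. The two statements differ in scope.

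**The case against.** The strongest reply is that the conflict is one of reading. Section 6.7.2 applies to leaving the study, whereas the pregnancy entry speaks of leaving treatment, and follow-up is then subject to judgement. Appendix E is invoked by section 6.4.3, so its contraindication already limits the biopsy. The discontinuation rule is worded as a recommendation, and the Week 24 list includes a pregnancy test and an ultrasound. An investigator who has read Appendix E is likely to follow it. The central laboratory manual, which describes how the biopsy is done, is not among the documents and may contain an exception.

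Part of this stands. Route A is one reading, not a certainty, and a biopsy in a known pregnancy is unlikely in practice. But Route B does not remove the conflict: the qualification governs entry to follow-up and not the procedures within it, and the Week 36 footnote is mandatory. Nor does the protocol say that Appendix E overrides the visit lists. An exception in a manual would still leave the protocol contradicting itself.

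A reader might also infer three stronger points, which the documents do not support.

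- **That Appendix E also rules out the DXA scan.** The contraindication concerns the Pipelle only, and no section restricts DXA in pregnancy.
- **That Week 48 wrongly lacks a pregnancy test.** That visit lists "BMD assessed by DXA for femoral neck, hip and spine. DXA can be performed ± 10 days from study visit" and no test, and section 6.6.1 says: "After the end of treatment period (end of week 24) until the end of follow-up period, no contraception is required". But nothing makes the test a condition for DXA. Tests are scheduled in 10 of the 11 columns of Appendix A, 7 of them without DXA. The scan may be done up to 10 days after baseline, or up to 10 days either side of the Week 12 and Week 24 visits, so it need not fall on the day of the test. The interval since the last test at Week 36 is 12 weeks by label but 309 − 253 = 56 days by the printed days. The absence of a Week 48 test contradicts no passage.
- **That pregnancies conceived after Week 36 go unrecorded, so that affected bone density values could not be identified.** Section 6.7.2.1 says that every pregnancy is to be reported, and no passage says that pregnancy affects the values. What remains is the difference in reporting scope.

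**Conclusion.** The point holds for the biopsy. For a woman discontinued for pregnancy, both routes in the protocol can reach a Pipelle biopsy, at Week 24 or at Week 36, without an exception for pregnancy, while Appendix E makes ongoing pregnancy an absolute contraindication. The sections where the conflict could have been settled, 6.7.2.2 and 8.6, do not settle it.

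The size cannot be given as a number of subjects, because the documents state no pregnancy rate; contraception is required during treatment for women of childbearing potential, so the group is probably small. The primary endpoint and its analysis are unaffected. The conclusion assumes that the visit lists are applied as written. For Route B it also assumes that follow-up is judged appropriate, that no biopsy was obtained at Week 24, and that the pregnancy is still ongoing at Week 36. The change should be made because it concerns safety and costs almost nothing, but it does not call the design into question.

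**What to change.** Reconcile sections 6.7.2, 6.7.2.1, 6.2.3.2 and 6.2.4.2 and Appendix A footnotes 2 and 3 with Appendix E, so that the biopsy requirement in the discontinuation and follow-up lists no longer contradicts the contraindication for a subject discontinued for pregnancy. State in section 6.7.2 or 6.7.2.1 which of the two routes such a subject follows. Section 6.7.2.2, now empty, is a natural place for a cross-reference. The clinical rule itself is for the sponsor to decide.

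In the same amendment, align the scope of pregnancy reporting between sections 6.7.2.1 and 8.6, so that sites know whether a pregnancy conceived after Week 36 is to be reported.

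The cost is amendment wording and a check that the site manuals agree. No visit, sample size or analysis changes.

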**6.7.2.1. Discontinuation criteria**

During the course of the study, the subject may be discontinued for the following reasons:

- **Lack of Efficacy:** Investigator's judgment only. If subject's opinion only, check subject's Request. Explain in the comment section of the eCRF Exit Form.
- **Adverse Event:** Includes clinically significant new or worsening existing condition as judged by the Investigator. Document in the AE form.
- **Subject's Request:** Consent withdrawal, subject moved, schedule conflicts, etc. Specify the reason in the comment section of the eCRF Exit Form.
- **Protocol Violation:** Major protocol violation which may affect the subject's safety. Specify the protocol violation in the comment section of the eCRF Exit Form.
- **Lost to Follow-up:** Document with two phone calls and a certified letter requesting return receipt without response. Document in the comment section of the eCRF Exit Form.
- **Pregnancy:** Subjects that have been exposed to study treatment and who become pregnant during the treatment period will be immediately withdrawn from treatment. Pregnancies that have been exposed to study treatment and occurred up to week 36, or started up to 4 weeks after treatment discontinuation in case of early withdrawal will be followed up for pregnancy and neonatal outcomes at birth. Any pregnancy must be reported with the Pregnancy Surveillance Form (see section 8.6).
- **Other:** Specify in the Comments section in the eCRF Exit Form. This reason should only be used if the reason for discontinuation is not better accounted for by another category.

Subjects who have an elevation of hepatic enzymes suspicious of drug induced liver toxicity according to the Food and Drug Administration (FDA) guidance on drug-induced liver injury (26), i.e. LFT increase > 3 x ULN associated with increased bilirubin > 1 x ULN, will be immediately withdrawn from treatment and followed up to return to normal of hepatic parameters.

All subjects withdrawn from treatment will enter – if appropriate – a 24-week follow-up period without treatment and continue daily eDiary recording up to Week 36 visit in order to continue to collect efficacy data.

**6.7.2.2. Follow-up for discontinued subjects**

Not applicable.

**6.7.3. Subject Replacement**

Discontinued subjects who received the study drug will not be replaced.

Discontinued subjects who did not receive the study drug may be replaced.

## 7. INVESTIGATIONAL MEDICINAL PRODUCT

### 7.1. DESCRIPTION OF INVESTIGATIONAL MEDICINAL PRODUCTS

The term “Investigational Medicinal Product” (IMP) will refer to either the ObsEva investigational drug or the placebo.

	Investigational product	Placebo
International nonproprietary name (INN)	NA	NA
Name of active ingredient	OBE2109	NA
Form	Film-coated tablet	Film-coated tablet
Strength	50mg, 75mg and 100mg	placebo
Dose or concentration of active treatment	50mg, 75mg, 100mg and 200mg	0mg
Route of administration	Oral	
Frequency of administration	Once daily for up to 24 weeks	
Manufacturer (Name and address)	Catalent Pharma Solutions [name]	
Packaging (primary and secondary)	PVC/Al blister with 7 tablets per blister, blister in two different colors (colored Al foil) for blinding purpose  Aluminum pouch	PVC/Al blister with 7 tablets per blister, blister in two different colors (colored Al foil) for blinding purpose  Aluminum pouch
Storage Requirements	As indicated on the study drug kit label	As indicated on the study drug kit label

## 7.2. DOSAGE AND ADMINISTRATION

### Investigational Medicinal Products (IMPs)

OBE2109 and placebo treatments will be supplied as film-coated tablets for oral administration.

The subjects will be given 3-monthly treatment packs.

OBE2109 and placebo oral tablet treatments will start on Day 1 between the first and the seventh day of menstruation and will be administered once daily, up to about 24 weeks. The subjects will take 2 tablets in the morning of each day as follows :

Treatment arm	Daily dose Part A Day 1 to Week 12		Daily dose Part B Week 12 to Week 24	
	Active tablet	Placebo tablet	Active tablet	Placebo tablet
50 mg	1 × 50 mg	1 × placebo	1 × 50 mg	1 × placebo
75 mg	1 × 75 mg	1 × placebo	1 × 75 mg	1 × placebo
100 mg	1 × 100 mg	1 × placebo	1 × 100 mg	1 × placebo
200 mg	2 × 100 mg	None	2 × 100 mg	None
Titrated arm	1 × 75 mg	1 × placebo	Titrated dose*	1 × placebo
Placebo/100 mg	None	2 × placebo	1 × 100 mg	1 × placebo

\* Dose titrated after 12 weeks based on the mean E2 levels analyzed at weeks 4 and 8 as follows:

- If  $E2 < 20$  pg/mL then reduce the dose to 50 mg daily
- If  $E2 > 50$  pg/mL then increase the dose to 100 mg daily
- If  $20 \leq E2 \leq 50$  pg/mL then dose remains at 75 mg per day

